2.2 Secondary outcome measures

- (i) Difference in time to extubation, intubation rate in patients on HFNO, re-intubation rate, ventilator free days at day 28, duration of ventilation, length of intensive care unit (ICU) and hospital stay as well as 28-day mortality, in the hyper-inflammatory and hypo-inflammatory phenotypes.
- (ii) Agreement of phenotype classification using a POC assay and commercially-available assays
- (iii) Agreement of phenotype classification using a POC assay and LCA
- (iv) Agreement of phenotype classification between baseline and day 3
- (v) Feasibility of delivering a POC assay in NHS/HSE intensive care setting as measured by assay technical failure rate.

- (vi) Frequency of inflammatory phenotypes in patients with AHRF and difference in outcomes as described for ARDS phenotypes.

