7.2 Secondary Outcomes

A secondary analysis for the outcome of 60 day mortality using logistic regression to adjust for important variables (age, site, and gender) will be carried out. Odds ratio (95% CI) and p value will be reported.

Differences in 60 day mortality will also be evaluated using phenotype allocation as defined by i) commercially available assays in conjunction with a parsimonious logistic regression model and ii) LCA. For each i) and ii), analyses will be conducted by calculating: a) absolute number and percentage by phenotype, b) unadjusted percentage point difference (95%, CI), c) risk ratio (95% CI), and d) p value from Pearson's chi-square test (95% CI).

Further secondary outcomes will be analysed using both POC-derived phenotype allocation and LCA-derived phenotype allocation.

For secondary outcomes based on dichotomous variables (Re-intubation rate, 28-day mortality), absolute number and percentage by phenotype will be calculated, and p-value will be from Pearson's chi-square test.

For continuous secondary outcomes (Ventilator free days at day 28; Duration of ventilation; Length of ICU stay; Length of hospital stay), data will be reported as median (IQR) with p value derived from Mann-Whitney U test.

Analyses will be conducted to assess agreement of phenotype classification methods. Comparisons will be made between: (i) POC-derived phenotype versus phenotype from commercially available assays (defined by up to 8 different parsimonious logistic regression models [5]), (ii) POC-derived phenotype versus LCA-derived phenotype, and (iii) POC-derived phenotype versus phenotype derived from clinical classifier machine learning algorithm [11]. Cohen's kappa coefficient (95% CI) will be calculated and p-value will be from McNemar's test for agreement. All of these analyses will be performed for phenotype allocation at day 0 and at day 3. For additional comparisons between classification methods, LCA phenotype will be selected as the "gold standard" and sensitivity, specificity, negative predictive value, and positive predictive value will be calculated for all other methods. Area under the receiver operating curve (AUC) will also be calculated. These analyses will also be performed for phenotype allocation at day 0 and day 3.

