7.4 Additional analysis

To study the performance of the New Global Definition of ARDS [12], primary and secondary outcomes will be reported for the entire study cohort, the study cohort stratified by ARDS severity as defined by the New Global Definition of ARDS [12], and the study cohort stratified by ARDS severity as defined by the Berlin Definition of ARDS [6].

An additional analysis will be conducted on the cohort of patients with AHRF, to assess the proportion of patients developing ARDS by phenotype. This will be reported as absolute number and percentage, with p value for difference between phenotypes from Fisher's exact test. In AHRF developing ARDS, the median (IQR) number of days to ARDS development will be calculated by phenotype, with p value for difference between phenotypes from Mann Whitney U test.

Outcomes will be compared within a given phenotype with respect to ARDS/AHRF diagnosis. Primary and secondary outcomes will be compared for all hyperinflammatory patients (ARDS vs. AHRF) and all hypoinflammatory patients (ARDS vs. AHRF). Comparisons will be made using Fisher's exact test for categorical outcomes and Mann-Whitney U Test for continuous outcomes.

Subsequent analyses after study completion may explore the relationship between hyperinflammatory and hypoinflammatory phenotypes and other ARDS phenotypes [13] and sepsis phenotypes [14,15] as well as the use of varying probability cutpoints for phenotype assignment in comparison to full latent class analysis.

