8.5 Study Outcomes

Primary outcome:

- Mortality at 60 days in patients with ARDS as defined by the POC assay, reported as n (%) by phenotype, unadjusted percentage point difference (95% CI), risk ratio (95% CI), and p value from Pearson's chi-square test

Secondary outcomes:

- Mortality at 60 days in patients with ARDS as defined by the POC assay, reported as odds ratio (95% CI) and p value from adjusted logistic regression (adjusted for age and gender)
- Mortality at 60 days in patients with ARDS defined by commercially-available laboratory assays and parsimonious models, reported as n (%) by phenotype, unadjusted percentage point difference (95%, CI), risk ratio (95% CI), and p value from Pearson's chi-square test (95% CI).

- Mortality at 60 days in patients with ARDS defined by the complete data-set using latent class analysis, reported as n (%) by phenotype, unadjusted percentage point difference (95% CI), risk ratio (95% CI), and p value from Pearson's chi-square test (95% CI).

For further secondary analyses, the assumption of normal distribution will be checked graphically for each continuous variable, but we anticipate using the following tests (alternative in brackets).

- Time to extubation, mean (SD) by phenotype, difference in means (95% CI) and p value from two-sided t-test for unpaired data (Mann-Whitney test)
- Intubation rate in patients receiving HFNO, number (%) by phenotype, percentage point difference (95% CI), and p value from chi-square test
- Re-intubation rate, number (%) by phenotype, percentage point difference (95% CI), and p value from chi-square test
- Ventilator free days at day 28, mean (SD) by phenotype, difference in means (95% CI) and p value from t-test for unpaired data (Mann-Whitney test)
- Duration of ventilation, mean (SD) by phenotype, difference in means (95% CI) and p value from t-test for unpaired data (Mann-Whitney test)
- Length of ICU stay, median (IQR) by phenotype, p value from Mann-Whitney test
- Length of hospital stay, median (IQR) by phenotype, p value from Mann-Whitney test
- 28-day mortality, n (%) by phenotype, unadjusted percentage point difference (95% CI) and Risk ratio (95% CI) and p value from chi-square
- Time to extubation, difference in means (95% CI) adjusted for age, co-morbidity, aetiology of ARDS, vasopressor requirement and PF ratio. P-values will be from ANCOVA.

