^a No. (%) for phenotypes and mean difference and risk ratio (95% CI) presented and unadjusted p-value from chi-square and adjusted p-value from logistic regression adjusted for age, gender, and site.

^b Mean(SD) for phenotypes and mean difference (95% CI) presented, unadjusted.

^c Median[IQR] and p-value from Mann-Whitney test.

Table x.x.x Secondary analyses

	Hyper-inflammatory phenotype n = (%)	Hypo-inflammatory phenotype n = (%)	Unadjusted % Point or Mean Difference (95% CI)	Unadjusted Risk ratio (95% CI)	p-value
Mortality at 60 days in patients with ARDS defined by commercially-available assays and parsimonious model					
Alive	N (xx.x%)	N (xx.x%)	xx.x (xx.x to xx.x)		
Dead	N (xx.x%)	N (xx.x%)	xx.x (xx.x to xx.x)	xx.x (xx.x to xx.x)	x.xxx
Mortality at 60 days in patients with ARDS defined by the complete data-set using latent class analysis					
Alive	N (xx.x%)	N (xx.x%)	xx.x (xx.x to xx.x)		
Dead	N (xx.x%)	N (xx.x%)	xx.x (xx.x to xx.x)	xx.x (xx.x to xx.x)	x.xxx
Secondary outcomes using phenotype allocation defined by the complete dataset using latent class analysis					
Time to extubation^b	xx.x (xx.x)	xx.x (xx.x)	xx.x (xx.x to xx.x)		x.xxx
Intubation rate^a	N (xx.x%)	N (xx.x%)	xx.x (xx.x to xx.x)		x.xxx
Re-intubation rate^a	N (xx.x%)	N (xx.x%)	xx.x (xx.x to xx.x)		x.xxx
Ventilator free days at day 28^b	xx.x (xx.x)	xx.x (xx.x)	xx.x (xx.x to xx.x)		x.xxx
Duration of ventilation^b	xx.x (xx.x)	xx.x (xx.x)	xx.x (xx.x to xx.x)		x.xxx
Length of ICU stay^c	xx.x [xx.x, xx.x]	xx.x [xx.x, xx.x]			x.xxx
Length of hospital stay^c	xx.x [xx.x, xx.x]	xx.x [xx.x, xx.x]			x.xxx
28-day mortality^a					
Alive	N (xx.x%)	N (xx.x%)	xx.x (xx.x to xx.x)		
Dead	N (xx.x%)	N (xx.x%)	xx.x (xx.x to xx.x)	xx.x (xx.x to xx.x)	x.xxx

No. (%) for phenotypes and mean difference and risk ratio (95% CI) presented.

Unadjusted p-value from chi-square.

Table x.x.x Agreement of phenotype classifications (Secondary outcomes)

	Hyper-inflammatory phenotype n = (%)	Hypo-inflammatory phenotype n = (%)	Cohen's kappa coefficient (95% CI)	p-value^a
Agreement of phenotype classification using a POC assay and commercially-available assay (model 1) [11]	N agreed= N disagreed=	N agreed= N disagreed=		
Agreement of phenotype classification using a POC assay and commercially-available assay (model 2) [11]	N agreed= N disagreed=	N agreed= N disagreed=		

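### Length of ICU and hospital stay are declared as a difference between phenotypes, but the plan gives them no between-phenotype estimate with a 95% CI

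*Supplement*

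**What the plan says.** SAP section 2.2(i) opens its list of clinical outcomes with "Difference in time to extubation, intubation rate in patients on HFNO, re-intubation rate, ventilator free days at day 28, duration of ventilation" and continues with "length of intensive care unit (ICU) and hospital stay as well as 28-day mortality, in the hyper-inflammatory and hypo-inflammatory phenotypes". Both stays are therefore declared as differences between phenotypes.

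The analysis of the two stays is specified in three places:

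- **Section 7.2**, for continuous secondary outcomes including both stays: "data will be reported as median (IQR) with p value derived from Mann-Whitney U test".
- **Section 8.5**: "Length of ICU stay, median (IQR) by phenotype, p value from Mann-Whitney test" and "Length of hospital stay, median (IQR) by phenotype, p value from Mann-Whitney test".
- **Appendix 1**, footnote c to the main clinical outcomes table: "Median[IQR] and p-value from Mann-Whitney test". The difference and risk ratio cells on both rows are blank.

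Section 4 counts both stays from ICU admission to discharge, or to death for a patient who dies before discharge.

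**The concern.** Two medians with IQRs and a p-value do not say which differences in stay the data support and which they rule out. The IQRs describe spread within each phenotype, not the precision of a contrast. The Mann-Whitney test is not a test of the difference between medians, so the gap between the two printed medians is not the quantity tested, and it has no interval.

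The study's hypothesis is that hyper-inflammatory patients do worse. For these two outcomes the planned output would show whether a rank test crossed 0.05, but not how far apart the phenotypes might plausibly be. With an assumed 3:1 split and a smaller group of about 116, a non-significant result could sit beside differences of several days that remain compatible with the data, and the reader could not see this.

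**Working it through.** **1. What 8.5 gives each clinical outcome in list 2.2(i)**

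| Outcome | Unadjusted between-phenotype estimate | Adjusted estimate |
|---|---|---|
| Time to extubation | difference in means, 95% CI | yes |
| Intubation rate on HFNO | percentage-point difference, 95% CI | yes |
| Re-intubation rate | percentage-point difference, 95% CI | yes |
| Ventilator free days | difference in means, 95% CI | yes |
| Duration of ventilation | difference in means, 95% CI | yes |
| 28-day mortality | percentage-point difference and risk ratio, 95% CI | yes |
| Length of ICU stay | none | none |
| Length of hospital stay | none | none |

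Section 7.2 alone would leave ventilator free days and duration of ventilation in the same position as the stays. Section 8.5 gives those two a difference in means with a CI, with the Mann-Whitney test as the bracketed alternative. The unconditional gap is therefore confined to the two stays.

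**2. Extent in the tables**

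Appendix 1 has nine cohorts: main, AHRF, mechanical ventilation, non-invasive ventilation, HFNO, HFNO at 30 L/min or more, COVID-19 excluded, samples within 24 h, and samples within 48 h. Each has one table of main outcomes by POC phenotype and one of secondary analyses that includes the LCA phenotype. So 9 × 2 = 18 tables and 18 × 2 = 36 stay rows, all with a blank difference cell.

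**3. Reproducing the plan's own design figure**

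No figure is stated for length of stay. The only design figure is the mortality calculation in section 5, which supplies the group sizes used below. A two-group test of 17% v 32% with 347 v 116 patients at two-sided 0.05 has power 0.912, against 90% stated. Inflation by N/(1 − 0.10) gives 347/0.9 = 386, 116/0.9 = 129 and 463/0.9 = 515, all as stated.

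**4. What an interval would show (illustration only)**

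Assumptions, none of them from the documents: log-normal stays with medians 10 v 12 days, SD of log 0.6, 0.8 or 1.0, and no deaths. Group sizes are those of section 5. The Hodges-Lehmann shift is the median of all 347 × 116 pairwise differences (hyper minus hypo). Its 95% limits are the ordered differences at rank about n₁n₂/2 ± 1.96·√[n₁n₂(n₁+n₂+1)/12].

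| SD of log | Mean shift (days) | CI half-width | CI width |
|---|---|---|---|
| 0.6 | 1.9 | 1.3 | about 2.6 |
| 0.8 | 1.8 | 1.7 | about 3.3 |
| 1.0 | 1.6 | 1.9 | about 3.9 |

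**5. Effect of counting stay to death**

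The run above ignores the definition in section 4. Applying the mortality assumed in section 5 (17% v 32%), with assumed death times that cut stay short, moves the mean shift from about 1.6 to 1.9 days to about −0.2 to 1.1 days. Mann-Whitney power moves from about 40–79% to about 5–43%. A repeat with log-normal death times (median 4 to 12 days, SD of log 0.8) gave the same picture. The shift and the power are thus driven largely by death times that the documents do not give. The need for an interval does not depend on them.

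**The case against.** **Median (IQR) with a Mann-Whitney test is a complete and common specification.** This stands in part. The analysis can be carried out as written, and the word difference in 2.2(i) heads a list and could be taken loosely as a comparison. But 8.5 gives the other six outcomes in that list an estimate with a CI, and no reason is offered for departing from this for the stays. Skewness justifies a rank test; it does not justify omitting the estimate that belongs to that test.

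**A reader might infer that the plan gives no idea of size at all.** That goes too far. Subtracting the printed medians gives a crude size in days. What is missing is a specified contrast and its precision.

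**A reader might extend the point to section 7.4**, where ARDS and AHRF are compared within each phenotype: "Comparisons will be made using Fisher's exact test for categorical outcomes and Mann-Whitney U Test for continuous outcomes". The documents do not support this. That section only names tests for an additional analysis. It does not limit what is reported, Appendix 1 has no tables for it, and 2.2 does not declare that comparison as a difference.

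**A reader might want a figure for how often a real difference would be missed.** None can be defended here, because the power depends so strongly on the assumed death times.

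**With stay ended at death, a shift in days is hard to interpret.** This stands as a caution: the shift mixes earlier discharge with earlier death. It applies equally to the p-value already planned, so it is a reason to label the estimate carefully, not to leave it out.

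**Conclusion.** The point holds for the two stay outcomes only. The declared outcome is a difference between phenotypes. The planned output in 7.2, 8.5 and all 36 table rows contains no between-phenotype estimate with a 95% CI, and nothing elsewhere in the SAP supplies one. The textual finding rests on no assumption.

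Its practical size cannot be derived from the documents. Under the illustrative assumptions (log-normal stays, medians 10 v 12 days, SD of log 0.6 to 1.0, 347 v 116) the unreported interval would be about 2.5 to 4 days wide, but the location of the shift depends heavily on death times.

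This is a minor reporting improvement. It concerns two components of one secondary outcome in an observational study and leaves the primary analysis and the sample size untouched.

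**What to change.** - In 7.2, 8.5 and footnote c of the Appendix 1 tables, report for both stays the Hodges-Lehmann shift in days (hyper- minus hypo-inflammatory) with its 95% CI, beside the Mann-Whitney p-value.
- Fill the blank difference cell on the stay rows of all 18 tables.
- Label the estimate as a shift, and note that it is not the difference between the two printed medians.
- State beside it that stay is counted to death, as defined in section 4, so that the shift reflects both earlier discharge and earlier death.

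The cost is SAP wording and a small addition to a rank analysis already planned. No extra data, patients or visits are needed. The one drawback is the extra labelling.

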APPENDIX 1: EXAMPLE SUMMARY TABLES

Table x.x.x.. Baseline Characteristics at study entry

	Hyper-inflammatory phenotype n = (%)	Hypo-inflammatory phenotype n = (%)	Total n = (%)
Age (years)	xx.x (xx.x)	xx.x (xx.x)	xx.x (xx.x)
Gender			
Male	N (xx.x%)	N (xx.x%)	N (xx.x%)
Female	N (xx.x%)	N (xx.x%)	N (xx.x%)
Ethnicity			
Caucasian	N (xx.x%)	N (xx.x%)	N (xx.x%)
Black	N (xx.x%)	N (xx.x%)	N (xx.x%)
Asian	N (xx.x%)	N (xx.x%)	N (xx.x%)
Unknown	N (xx.x%)	N (xx.x%)	N (xx.x%)
Other	N (xx.x%)	N (xx.x%)	N (xx.x%)
Height (cm)	xx.x (xx.x)	xx.x (xx.x)	xx.x (xx.x)
Weight (kg)	xx.x (xx.x)	xx.x (xx.x)	xx.x (xx.x)
Predicted body weight (kg)	xx.x (xx.x)	xx.x (xx.x)	xx.x (xx.x)
Body mass index (kg/m²)	xx.x (xx.x)	xx.x (xx.x)	xx.x (xx.x)
Cigarette smoking status			
Current smoker	N (xx.x%)	N (xx.x%)	N (xx.x%)
Past smoker	N (xx.x%)	N (xx.x%)	N (xx.x%)
Never smoked	N (xx.x%)	N (xx.x%)	N (xx.x%)
Current smokers			
Number of years smoked	xx.x (xx.x)	xx.x (xx.x)	xx.x (xx.x)
Average smoked per day	xx.x (xx.x)	xx.x (xx.x)	xx.x (xx.x)
Not known	N (xx.x%)	N (xx.x%)	N (xx.x%)
Past smokers			

Number of years smoked	xx.x (xx.x)	xx.x (xx.x)	xx.x (xx.x)
Average smoked per day	xx.x (xx.x)	xx.x (xx.x)	xx.x (xx.x)
Not known	N (xx.x%)	N (xx.x%)	N (xx.x%)
Number of years e-smoking	xx.x (xx.x)	xx.x (xx.x)	xx.x (xx.x)
Type of e-smoking device			
Disposable	N (xx.x%)	N (xx.x%)	N (xx.x%)
Refillable	N (xx.x%)	N (xx.x%)	N (xx.x%)
Voltage variable	N (xx.x%)	N (xx.x%)	N (xx.x%)
Other	N (xx.x%)	N (xx.x%)	N (xx.x%)
Not known	N (xx.x%)	N (xx.x%)	N (xx.x%)
Amount of e-liquid used per day (mls)			
0-4 mls	N (xx.x%)	N (xx.x%)	N (xx.x%)
5-9 mls	N (xx.x%)	N (xx.x%)	N (xx.x%)
10-14 mls	N (xx.x%)	N (xx.x%)	N (xx.x%)
15-19 mls	N (xx.x%)	N (xx.x%)	N (xx.x%)
20+ mls	N (xx.x%)	N (xx.x%)	N (xx.x%)
Other	N (xx.x%)	N (xx.x%)	N (xx.x%)
Does the e-liquid used by the patient contain nicotine?			
Yes	N (xx.x%)	N (xx.x%)	N (xx.x%)
No	N (xx.x%)	N (xx.x%)	N (xx.x%)
Nicotine content of e-liquid (Per Week)			
5mg/ml	N (xx.x%)	N (xx.x%)	N (xx.x%)
10mg/ml	N (xx.x%)	N (xx.x%)	N (xx.x%)
15mg/ml	N (xx.x%)	N (xx.x%)	N (xx.x%)
20mg/ml	N (xx.x%)	N (xx.x%)	N (xx.x%)
Other	N (xx.x%)	N (xx.x%)	N (xx.x%)
Not Known	N (xx.x%)	N (xx.x%)	N (xx.x%)
Past e-smokers			
Number of years e-smoking	xx.x (xx.x)	xx.x (xx.x)	xx.x (xx.x)
Number of years since stopped e-smoking	xx.x (xx.x)	xx.x (xx.x)	xx.x (xx.x)
Not known	N (xx.x%)	N (xx.x%)	N (xx.x%)
Alcohol use			
Yes	N (xx.x%)	N (xx.x%)	N (xx.x%)
No	N (xx.x%)	N (xx.x%)	N (xx.x%)
Average units of alcohol consumed per week	xx.x (xx.x)	xx.x (xx.x)	xx.x (xx.x)

Co-morbidities (Yes results)			
Congestive Heart Failure	N (xx.x%)	N (xx.x%)	N (xx.x%)
Myocardial Infarction	N (xx.x%)	N (xx.x%)	N (xx.x%)
COPD	N (xx.x%)	N (xx.x%)	N (xx.x%)
Asthma	N (xx.x%)	N (xx.x%)	N (xx.x%)
Diabetes	N (xx.x%)	N (xx.x%)	N (xx.x%)
Chronic Liver Disease	N (xx.x%)	N (xx.x%)	N (xx.x%)
Cancer	N (xx.x%)	N (xx.x%)	N (xx.x%)
Chronic Renal Failure	N (xx.x%)	N (xx.x%)	N (xx.x%)
Other	N (xx.x%)	N (xx.x%)	N (xx.x%)
Aetiology of ARDS			
Smoke/toxin inhalation	N (xx.x%)	N (xx.x%)	N (xx.x%)
Gastric content aspiration	N (xx.x%)	N (xx.x%)	N (xx.x%)
Near drowning	N (xx.x%)	N (xx.x%)	N (xx.x%)
Thoracic trauma	N (xx.x%)	N (xx.x%)	N (xx.x%)
Pneumonia	N (xx.x%)	N (xx.x%)	N (xx.x%)
Sepsis	N (xx.x%)	N (xx.x%)	N (xx.x%)
Cardiopulmonary bypass	N (xx.x%)	N (xx.x%)	N (xx.x%)
Pancreatitis	N (xx.x%)	N (xx.x%)	N (xx.x%)
Non-thoracic trauma	N (xx.x%)	N (xx.x%)	N (xx.x%)
Other	N (xx.x%)	N (xx.x%)	N (xx.x%)
APACHE II score	xx.x (xx.x)	xx.x (xx.x)	xx.x (xx.x)
Vital Signs			
Temperature (°C)	xx.x (xx.x)	xx.x (xx.x)	xx.x (xx.x)
Heart rate (bpm)	xx.x (xx.x)	xx.x (xx.x)	xx.x (xx.x)
Systolic blood pressure (mmHg)	xx.x (xx.x)	xx.x (xx.x)	xx.x (xx.x)
Diastolic blood pressure (mmHg)	xx.x (xx.x)	xx.x (xx.x)	xx.x (xx.x)
Haematology			
Haematocrit (L/L)	xx.x (xx.x)	xx.x (xx.x)	xx.x (xx.x)
White Cell Count (x10 ⁹ /L)	xx.x (xx.x)	xx.x (xx.x)	xx.x (xx.x)
PT (s)	xx.x (xx.x)	xx.x (xx.x)	xx.x (xx.x)
Fibrinogen (g/L)	xx.x (xx.x)	xx.x (xx.x)	xx.x (xx.x)
Biochemistry			
Sodium (mmol/L)	xx.x (xx.x)	xx.x (xx.x)	xx.x (xx.x)
Glucose (mmol/L)	xx.x (xx.x)	xx.x (xx.x)	xx.x (xx.x)
Albumin (g/L)	xx.x (xx.x)	xx.x (xx.x)	xx.x (xx.x)

AST (U/L)	xx.x (xx.x)	xx.x (xx.x)	xx.x (xx.x)
ALT (U/L)	xx.x (xx.x)	xx.x (xx.x)	xx.x (xx.x)
First qualifying P/F ratio	xx.x (xx.x)	xx.x (xx.x)	xx.x (xx.x)
Worst P/F Ratio	xx.x (xx.x)	xx.x (xx.x)	xx.x (xx.x)
P/F Ratio closest to but prior to patient recruitment	xx.x (xx.x)	xx.x (xx.x)	xx.x (xx.x)
pH	xx.x (xx.x)	xx.x (xx.x)	xx.x (xx.x)
Lactate	xx.x (xx.x)	xx.x (xx.x)	xx.x (xx.x)
Bicarbonate	xx.x (xx.x)	xx.x (xx.x)	xx.x (xx.x)
PaCO₂	xx.x (xx.x)	xx.x (xx.x)	xx.x (xx.x)
PaO₂	xx.x (xx.x)	xx.x (xx.x)	xx.x (xx.x)
FiO₂	xx.x (xx.x)	xx.x (xx.x)	xx.x (xx.x)
Mode of Ventilation			
SIMV	N (xx.x%)	N (xx.x%)	N (xx.x%)
APRV	N (xx.x%)	N (xx.x%)	N (xx.x%)
HFOV	N (xx.x%)	N (xx.x%)	N (xx.x%)
BIPAP	N (xx.x%)	N (xx.x%)	N (xx.x%)
PC	N (xx.x%)	N (xx.x%)	N (xx.x%)
PRVC	N (xx.x%)	N (xx.x%)	N (xx.x%)
PS	N (xx.x%)	N (xx.x%)	N (xx.x%)
NIV	N (xx.x%)	N (xx.x%)	N (xx.x%)
HFNO	N (xx.x%)	N (xx.x%)	N (xx.x%)
CPAP/ASB	N (xx.x%)	N (xx.x%)	N (xx.x%)
Other	N (xx.x%)	N (xx.x%)	N (xx.x%)
None	N (xx.x%)	N (xx.x%)	N (xx.x%)
Minute Volume (ml)	xx.x (xx.x)	xx.x (xx.x)	xx.x (xx.x)
Total Respiratory Rate	xx.x (xx.x)	xx.x (xx.x)	xx.x (xx.x)
Mean Airway Pressure (cmH2O)	xx.x (xx.x)	xx.x (xx.x)	xx.x (xx.x)
Plateau Pressure (cmH2O)	xx.x (xx.x)	xx.x (xx.x)	xx.x (xx.x)
PEEP (cmH2O)	xx.x (xx.x)	xx.x (xx.x)	xx.x (xx.x)
Tidal Volume (Minute Volume/Total Respiratory Rate)	xx.x (xx.x)	xx.x (xx.x)	xx.x (xx.x)
Tidal Volume (mls/kg PBW)	xx.x (xx.x)	xx.x (xx.x)	xx.x (xx.x)
Respiratory Compliance (ml/cmH2O)	xx.x (xx.x)	xx.x (xx.x)	xx.x (xx.x)
Oxygenation Index (OI)	xx.x (xx.x)	xx.x (xx.x)	xx.x (xx.x)
Total SOFA score	xx.x (xx.x)	xx.x (xx.x)	xx.x (xx.x)
Use of Adjunctive Therapies			
Airway Pressure Release Ventilation (APRV)	N (xx.x%)	N (xx.x%)	N (xx.x%)

High-Frequency Oscillatory Ventilation (HFOV)	N (xx.x%)	N (xx.x%)	N (xx.x%)
Neuromuscular Blocking Drugs (NMBD)	N (xx.x%)	N (xx.x%)	N (xx.x%)
Nitric Oxide	N (xx.x%)	N (xx.x%)	N (xx.x%)
Prone Position	N (xx.x%)	N (xx.x%)	N (xx.x%)
ECCO2R	N (xx.x%)	N (xx.x%)	N (xx.x%)
Other	N (xx.x%)	N (xx.x%)	N (xx.x%)
Murray Lung Injury Score	xx.x (xx.x)	xx.x (xx.x)	xx.x (xx.x)
Steroid Treatment on day 0			
Yes	N (xx.x%)	N (xx.x%)	N (xx.x%)
No	N (xx.x%)	N (xx.x%)	N (xx.x%)
Type of steroid used			
Hydrocortisone	N (xx.x%)	N (xx.x%)	N (xx.x%)
Prednisolone	N (xx.x%)	N (xx.x%)	N (xx.x%)
Dexamethasone	N (xx.x%)	N (xx.x%)	N (xx.x%)
Methylprednisolone	N (xx.x%)	N (xx.x%)	N (xx.x%)
Fludrocortisone	N (xx.x%)	N (xx.x%)	N (xx.x%)
Other	N (xx.x%)	N (xx.x%)	N (xx.x%)
Total daily steroid dose	xx.x (xx.x)	xx.x (xx.x)	xx.x (xx.x)
Statin Treatment on day 0 or within last 7 days			
Yes	N (xx.x%)	N (xx.x%)	N (xx.x%)
No	N (xx.x%)	N (xx.x%)	N (xx.x%)
Type of statin used			
Pravastatin	N (xx.x%)	N (xx.x%)	N (xx.x%)
Atorvastatin	N (xx.x%)	N (xx.x%)	N (xx.x%)
Simvastatin	N (xx.x%)	N (xx.x%)	N (xx.x%)
Rosuvastatin	N (xx.x%)	N (xx.x%)	N (xx.x%)
Other	N (xx.x%)	N (xx.x%)	N (xx.x%)
Total daily statin dose	xx.x (xx.x)	xx.x (xx.x)	xx.x (xx.x)
Insulin Treatment on day 0			
Yes	N (xx.x%)	N (xx.x%)	N (xx.x%)
No	N (xx.x%)	N (xx.x%)	N (xx.x%)
Total daily insulin dose	xx.x (xx.x)	xx.x (xx.x)	xx.x (xx.x)
Enteral feeding on day 0			
Yes	N (xx.x%)	N (xx.x%)	N (xx.x%)
No	N (xx.x%)	N (xx.x%)	N (xx.x%)
Total daily calories given	xx.x (xx.x)	xx.x (xx.x)	xx.x (xx.x)

Child Pugh Score	xx.x (xx.x)	xx.x (xx.x)	xx.x (xx.x)
Renal replacement therapy			
Yes	N (xx.x%)	N (xx.x%)	N (xx.x%)
No	N (xx.x%)	N (xx.x%)	N (xx.x%)
Does the patient have COVID-19?			
Yes	N (xx.x%)	N (xx.x%)	N (xx.x%)
No	N (xx.x%)	N (xx.x%)	N (xx.x%)
How was COVID-19 diagnosed?			
Clinical diagnosis	N (xx.x%)	N (xx.x%)	N (xx.x%)
PCR diagnosis	N (xx.x%)	N (xx.x%)	N (xx.x%)

Mean (SD) presented for continuous variables and no. (%) for all categorical variables.

Table x.x.x. Withdrawal

	Hyper-inflammatory phenotype n = (%)	Hypo-inflammatory phenotype n = (%)
Withdrawal of consent	N (xx.x%)	N (xx.x%)
Use of data already collected	N (xx.x%)	N (xx.x%)
Ongoing data collection during hospital admission	N (xx.x%)	N (xx.x%)
Long term storage of research samples	N (xx.x%)	N (xx.x%)
Confirmation of vital status	N (xx.x%)	N (xx.x%)

Table x.x.x Protocol Deviations

	Number of Events			Number of Patients		
	Total N= (%)	Hyper-inflammatory phenotype n = (%)	Hypo-inflammatory phenotype n = (%)	Total N= (%)	Hyper-inflammatory phenotype n = (%)	Hypo-inflammatory phenotype n = (%)
Eligibility						
Consent						
Sample Not Taken						
POC Assay Result Not Available						
Other						

Table x.x.x Main Clinical Outcome variables

	Hyper-inflammatory phenotype n = (%)	Hypo-inflammatory phenotype n = (%)	Unadjusted % Point or Mean Difference (95% CI)	Unadjusted risk ratio (95% CI)	p-value	Adjusted odds ratio (95% CI)	p-value
Primary outcome ^a							
Mortality at 60 days in patients with ARDS as defined by the POC assay							
Alive	N (xx.x%)	N (xx.x%)	xx.x (xx.x to xx.x)				
Dead	N (xx.x%)	N (xx.x%)	xx.x (xx.x to xx.x)	xx.x (xx.x to xx.x)	x.xxx		
Secondary outcomes							
Adjusted 60-day mortality (phenotype defined by POC assay)						xx.x (xx.x to xx.x)	x.xxx
Time to extubation ^b	xx.x (xx.x)	xx.x (xx.x)	xx.x (xx.x to xx.x)		x.xxx		x.xxx
Intubation rate^a	N (xx.x%)	N (xx.x%)	xx.x (xx.x to xx.x)		x.xxx		x.xxx
Re-intubation rate ^a	N (xx.x%)	N (xx.x%)	xx.x (xx.x to xx.x)		x.xxx		x.xxx
Ventilator free days at day 28 ^b	xx.x (xx.x)	xx.x (xx.x)	xx.x (xx.x to xx.x)		x.xxx		x.xxx
Duration of ventilation ^b	xx.x (xx.x)	xx.x (xx.x)	xx.x (xx.x to xx.x)		x.xxx		x.xxx
Length of ICU stay ^c	xx.x [xx.x, xx.x]	xx.x [xx.x, xx.x]			x.xxx		
Length of hospital stay ^c	xx.x [xx.x, xx.x]	xx.x [xx.x, xx.x]			x.xxx		
28-day mortality ^a							
Alive	N (xx.x%)	N (xx.x%)	xx.x (xx.x to xx.x)				
Dead	N (xx.x%)	N (xx.x%)	xx.x (xx.x to xx.x)	xx.x (xx.x to xx.x)	x.xxx	xx.x (xx.x to xx.x)	x.xxx

^a No. (%) for phenotypes and mean difference and risk ratio (95% CI) presented and unadjusted p-value from chi-square and adjusted p-value from logistic regression adjusted for age, gender, and site.

^b Mean(SD) for phenotypes and mean difference (95% CI) presented, unadjusted.

^c Median[IQR] and p-value from Mann-Whitney test.

Table x.x.x Secondary analyses

	Hyper-inflammatory phenotype n = (%)	Hypo-inflammatory phenotype n = (%)	Unadjusted % Point or Mean Difference (95% CI)	Unadjusted Risk ratio (95% CI)	p-value
Mortality at 60 days in patients with ARDS defined by commercially-available assays and parsimonious model					
Alive	N (xx.x%)	N (xx.x%)	xx.x (xx.x to xx.x)		
Dead	N (xx.x%)	N (xx.x%)	xx.x (xx.x to xx.x)	xx.x (xx.x to xx.x)	x.xxx
Mortality at 60 days in patients with ARDS defined by the complete data-set using latent class analysis					
Alive	N (xx.x%)	N (xx.x%)	xx.x (xx.x to xx.x)		
Dead	N (xx.x%)	N (xx.x%)	xx.x (xx.x to xx.x)	xx.x (xx.x to xx.x)	x.xxx
Secondary outcomes using phenotype allocation defined by the complete dataset using latent class analysis					
Time to extubation^b	xx.x (xx.x)	xx.x (xx.x)	xx.x (xx.x to xx.x)		x.xxx
Intubation rate^a	N (xx.x%)	N (xx.x%)	xx.x (xx.x to xx.x)		x.xxx
Re-intubation rate^a	N (xx.x%)	N (xx.x%)	xx.x (xx.x to xx.x)		x.xxx
Ventilator free days at day 28^b	xx.x (xx.x)	xx.x (xx.x)	xx.x (xx.x to xx.x)		x.xxx
Duration of ventilation^b	xx.x (xx.x)	xx.x (xx.x)	xx.x (xx.x to xx.x)		x.xxx
Length of ICU stay^c	xx.x [xx.x, xx.x]	xx.x [xx.x, xx.x]			x.xxx
Length of hospital stay^c	xx.x [xx.x, xx.x]	xx.x [xx.x, xx.x]			x.xxx
28-day mortality^a					
Alive	N (xx.x%)	N (xx.x%)	xx.x (xx.x to xx.x)		
Dead	N (xx.x%)	N (xx.x%)	xx.x (xx.x to xx.x)	xx.x (xx.x to xx.x)	x.xxx

No. (%) for phenotypes and mean difference and risk ratio (95% CI) presented.

Unadjusted p-value from chi-square.

Table x.x.x Agreement of phenotype classifications (Secondary outcomes)

	Hyper-inflammatory phenotype n = (%)	Hypo-inflammatory phenotype n = (%)	Cohen's kappa coefficient (95% CI)	p-value^a
Agreement of phenotype classification using a POC assay and commercially-available assay (model 1) [11]	N agreed= N disagreed=	N agreed= N disagreed=		
Agreement of phenotype classification using a POC assay and commercially-available assay (model 2) [11]	N agreed= N disagreed=	N agreed= N disagreed=		
Agreement of phenotype classification using a POC assay and commercially-available assay (model 3) [11]	N agreed= N disagreed=	N agreed= N disagreed=		
Agreement of phenotype classification using a POC assay and commercially-available assay (model 4) [11]	N agreed= N disagreed=	N agreed= N disagreed=		
Agreement of phenotype classification using a POC assay and commercially-available assay (model 5) [11]	N agreed= N disagreed=	N agreed= N disagreed=		
Agreement of phenotype classification using a POC assay and commercially-available assay (model 6) [11]	N agreed= N disagreed=	N agreed= N disagreed=		
Agreement of phenotype classification using a POC assay and commercially-available assay (model 7) [11]	N agreed= N disagreed=	N agreed= N disagreed=		
Agreement of phenotype classification using a POC assay and commercially-available assay (model 8) [11]	N agreed= N disagreed=	N agreed= N disagreed=		
Agreement of phenotype classification using a POC-derived phenotype and LCA-derived phenotype	N agreed= N disagreed=	N agreed= N disagreed=		
Agreement of phenotype classification between day 1 and 3	N agreed= N disagreed=	N agreed= N disagreed=		

^a p-value from McNemar's test used for agreement.

Table x.x.x Sensitivity analysis of the main clinical outcomes in patients with AHRF

	Hyper-inflammatory phenotype n = (%)	Hypo-inflammatory phenotype n = (%)	Unadjusted % Point or Mean Difference (95% CI)	Unadjusted risk ratio (95% CI)	p-value	Adjusted odds ratio (95% CI)	p-value
Primary outcome ^a							
Mortality at 60 days in patients with ARDS as defined by the POC assay							
Alive	N (xx.x%)	N (xx.x%)	xx.x (xx.x to xx.x)				
Dead	N (xx.x%)	N (xx.x%)	xx.x (xx.x to xx.x)	xx.x (xx.x to xx.x)	x.xxx		
Secondary outcomes							
Adjusted 60-day mortality (phenotype defined by POC assay)						xx.x (xx.x to xx.x)	x.xxx
Time to extubation ^b	xx.x (xx.x)	xx.x (xx.x)	xx.x (xx.x to xx.x)		x.xxx		x.xxx
Intubation rate^a	N (xx.x%)	N (xx.x%)	xx.x (xx.x to xx.x)		x.xxx		x.xxx
Re-intubation rate ^a	N (xx.x%)	N (xx.x%)	xx.x (xx.x to xx.x)		x.xxx		x.xxx
Ventilator free days at day 28 ^b	xx.x (xx.x)	xx.x (xx.x)	xx.x (xx.x to xx.x)		x.xxx		x.xxx
Duration of ventilation ^b	xx.x (xx.x)	xx.x (xx.x)	xx.x (xx.x to xx.x)		x.xxx		x.xxx
Length of ICU stay ^c	xx.x [xx.x, xx.x]	xx.x [xx.x, xx.x]			x.xxx		
Length of hospital stay ^c	xx.x [xx.x, xx.x]	xx.x [xx.x, xx.x]			x.xxx		
28-day mortality ^a							
Alive	N (xx.x%)	N (xx.x%)	xx.x (xx.x to xx.x)				
Dead	N (xx.x%)	N (xx.x%)	xx.x (xx.x to xx.x)	xx.x (xx.x to xx.x)	x.xxx	xx.x (xx.x to xx.x)	x.xxx

^a No. (%) for phenotypes and mean difference and risk ratio (95% CI) presented and unadjusted p-value from chi-square and adjusted p-value from logistic regression adjusted for age, gender, and site.

^b Mean(SD) for phenotypes and mean difference (95% CI) presented, unadjusted.

^c Median[IQR] and p-value from Mann-Whitney test.

Table x.x.x Secondary analyses, AHRF cohort

	Hyper-inflammatory phenotype n = (%)	Hypo-inflammatory phenotype n = (%)	Unadjusted % Point or Mean Difference (95% CI)	Unadjusted Risk ratio (95% CI)	p-value
Mortality at 60 days in patients with AHRF defined by commercially-available assays and parsimonious model					
Alive	N (xx.x%)	N (xx.x%)	xx.x (xx.x to xx.x)		
Dead	N (xx.x%)	N (xx.x%)	xx.x (xx.x to xx.x)	xx.x (xx.x to xx.x)	x.xxx
Mortality at 60 days in patients with AHRF defined by the complete data-set using latent class analysis					
Alive	N (xx.x%)	N (xx.x%)	xx.x (xx.x to xx.x)		
Dead	N (xx.x%)	N (xx.x%)	xx.x (xx.x to xx.x)	xx.x (xx.x to xx.x)	x.xxx
Secondary outcomes using phenotype allocation defined by the complete dataset using latent class analysis					
Time to extubation ^b	xx.x (xx.x)	xx.x (xx.x)	xx.x (xx.x to xx.x)		x.xxx
Intubation rate ^a	N (xx.x%)	N (xx.x%)	xx.x (xx.x to xx.x)		x.xxx
Re-intubation rate ^a	N (xx.x%)	N (xx.x%)	xx.x (xx.x to xx.x)		x.xxx
Ventilator free days at day 28 ^b	xx.x (xx.x)	xx.x (xx.x)	xx.x (xx.x to xx.x)		x.xxx
Duration of ventilation ^b	xx.x (xx.x)	xx.x (xx.x)	xx.x (xx.x to xx.x)		x.xxx
Length of ICU stay ^c	xx.x [xx.x, xx.x]	xx.x [xx.x, xx.x]			x.xxx
Length of hospital stay ^c	xx.x [xx.x, xx.x]	xx.x [xx.x, xx.x]			x.xxx
28-day mortality ^a					
Alive	N (xx.x%)	N (xx.x%)	xx.x (xx.x to xx.x)		
Dead	N (xx.x%)	N (xx.x%)	xx.x (xx.x to xx.x)	xx.x (xx.x to xx.x)	x.xxx

No. (%) for phenotypes and mean difference and risk ratio (95% CI) presented.
Unadjusted p-value from chi-square.

Table x.x.x Sensitivity analysis of the main clinical outcomes in patients receiving mechanical ventilation

	Hyper-inflammatory phenotype n = (%)	Hypo-inflammatory phenotype n = (%)	Unadjusted % Point or Mean Difference (95% CI)	Unadjusted risk ratio (95% CI)	p-value	Adjusted odds ratio (95% CI)	p-value
Primary outcome ^a							
Mortality at 60 days in patients with ARDS as defined by the POC assay							
Alive	N (xx.x%)	N (xx.x%)	xx.x (xx.x to xx.x)				
Dead	N (xx.x%)	N (xx.x%)	xx.x (xx.x to xx.x)	xx.x (xx.x to xx.x)	x.xxx		
Secondary outcomes							
Adjusted 60-day mortality (phenotype defined by POC assay)						xx.x (xx.x to xx.x)	x.xxx
Time to extubation ^b	xx.x (xx.x)	xx.x (xx.x)	xx.x (xx.x to xx.x)		x.xxx		x.xxx
Re-intubation rate ^a	N (xx.x%)	N (xx.x%)	xx.x (xx.x to xx.x)		x.xxx		x.xxx
Ventilator free days at day 28 ^b	xx.x (xx.x)	xx.x (xx.x)	xx.x (xx.x to xx.x)		x.xxx		x.xxx
Duration of ventilation ^b	xx.x (xx.x)	xx.x (xx.x)	xx.x (xx.x to xx.x)		x.xxx		x.xxx
Length of ICU stay ^c	xx.x [xx.x, xx.x]	xx.x [xx.x, xx.x]			x.xxx		
Length of hospital stay ^c	xx.x [xx.x, xx.x]	xx.x [xx.x, xx.x]			x.xxx		
28-day mortality ^a							
Alive	N (xx.x%)	N (xx.x%)	xx.x (xx.x to xx.x)				
Dead	N (xx.x%)	N (xx.x%)	xx.x (xx.x to xx.x)	xx.x (xx.x to xx.x)	x.xxx	xx.x (xx.x to xx.x)	x.xxx

^a No. (%) for phenotypes and mean difference and risk ratio (95% CI) presented and unadjusted p-value from chi-square and adjusted p-value from logistic regression adjusted for age, gender, and site.

^b Mean(SD) for phenotypes and mean difference (95% CI) presented, unadjusted.

^c Median[IQR] and p-value from Mann-Whitney test.

Table x.x.x Secondary analyses, mechanical ventilation cohort

	Hyper-inflammatory phenotype n = (%)	Hypo-inflammatory phenotype n = (%)	Unadjusted % Point or Mean Difference (95% CI)	Unadjusted Risk ratio (95% CI)	p-value
Mortality at 60 days in patients with ARDS defined by commercially-available assays and parsimonious model					
Alive	N (xx.x%)	N (xx.x%)	xx.x (xx.x to xx.x)		
Dead	N (xx.x%)	N (xx.x%)	xx.x (xx.x to xx.x)	xx.x (xx.x to xx.x)	x.xxx
Mortality at 60 days in patients with ARDS defined by the complete data-set using latent class analysis					
Alive	N (xx.x%)	N (xx.x%)	xx.x (xx.x to xx.x)		
Dead	N (xx.x%)	N (xx.x%)	xx.x (xx.x to xx.x)	xx.x (xx.x to xx.x)	x.xxx
Secondary outcomes using phenotype allocation defined by the complete dataset using latent class analysis					
Time to extubation^b	xx.x (xx.x)	xx.x (xx.x)	xx.x (xx.x to xx.x)		x.xxx
Intubation rate^a	N (xx.x%)	N (xx.x%)	xx.x (xx.x to xx.x)		x.xxx
Re-intubation rate^a	N (xx.x%)	N (xx.x%)	xx.x (xx.x to xx.x)		x.xxx
Ventilator free days at day 28^b	xx.x (xx.x)	xx.x (xx.x)	xx.x (xx.x to xx.x)		x.xxx
Duration of ventilation^b	xx.x (xx.x)	xx.x (xx.x)	xx.x (xx.x to xx.x)		x.xxx
Length of ICU stay^c	xx.x [xx.x, xx.x]	xx.x [xx.x, xx.x]			x.xxx
Length of hospital stay^c	xx.x [xx.x, xx.x]	xx.x [xx.x, xx.x]			x.xxx
28-day mortality^a					
Alive	N (xx.x%)	N (xx.x%)	xx.x (xx.x to xx.x)		
Dead	N (xx.x%)	N (xx.x%)	xx.x (xx.x to xx.x)	xx.x (xx.x to xx.x)	x.xxx

No. (%) for phenotypes and mean difference and risk ratio (95% CI) presented.

Unadjusted p-value from chi-square.

Table x.x.x Sensitivity analysis of the main clinical outcomes in patients receiving non-invasive ventilation

	Hyper-inflammatory phenotype n = (%)	Hypo-inflammatory phenotype n = (%)	Unadjusted % Point or Mean Difference (95% CI)	Unadjusted risk ratio (95% CI)	p-value	Adjusted odds ratio (95% CI)	p-value
Primary outcome ^a							
Mortality at 60 days in patients with ARDS as defined by the POC assay							
Alive	N (xx.x%)	N (xx.x%)	xx.x (xx.x to xx.x)				
Dead	N (xx.x%)	N (xx.x%)	xx.x (xx.x to xx.x)	xx.x (xx.x to xx.x)	x.xxx		
Secondary outcomes							
Adjusted 60-day mortality (phenotype defined by POC assay)						xx.x (xx.x to xx.x)	x.xxx
Intubation rate^a	N (xx.x%)	N (xx.x%)	xx.x (xx.x to xx.x)		x.xxx		x.xxx
Re-intubation rate ^a	N (xx.x%)	N (xx.x%)	xx.x (xx.x to xx.x)		x.xxx		x.xxx
Ventilator free days at day 28 ^b	xx.x (xx.x)	xx.x (xx.x)	xx.x (xx.x to xx.x)		x.xxx		x.xxx
Duration of ventilation ^b	xx.x (xx.x)	xx.x (xx.x)	xx.x (xx.x to xx.x)		x.xxx		x.xxx
Length of ICU stay ^c	xx.x [xx.x, xx.x]	xx.x [xx.x, xx.x]			x.xxx		
Length of hospital stay ^c	xx.x [xx.x, xx.x]	xx.x [xx.x, xx.x]			x.xxx		
28-day mortality ^a							
Alive	N (xx.x%)	N (xx.x%)	xx.x (xx.x to xx.x)				
Dead	N (xx.x%)	N (xx.x%)	xx.x (xx.x to xx.x)	xx.x (xx.x to xx.x)	x.xxx	xx.x (xx.x to xx.x)	x.xxx

^a No. (%) for phenotypes and mean difference and risk ratio (95% CI) presented and unadjusted p-value from chi-square and adjusted p-value from logistic regression adjusted for age, gender, and site.

^b Mean(SD) for phenotypes and mean difference (95% CI) presented, unadjusted.

^c Median[IQR] and p-value from Mann-Whitney test.

Table x.x.x Secondary analyses, non-invasive ventilation cohort

	Hyper-inflammatory phenotype n = (%)	Hypo-inflammatory phenotype n = (%)	Unadjusted % Point or Mean Difference (95% CI)	Unadjusted Risk ratio (95% CI)	p-value
Mortality at 60 days in patients with ARDS defined commercially-available assays and parsimonious model					
Alive	N (xx.x%)	N (xx.x%)	xx.x (xx.x to xx.x)		
Dead	N (xx.x%)	N (xx.x%)	xx.x (xx.x to xx.x)	xx.x (xx.x to xx.x)	x.xxx
Mortality at 60 days in patients with ARDS defined by the complete data-set using latent class analysis					
Alive	N (xx.x%)	N (xx.x%)	xx.x (xx.x to xx.x)		
